1. BACKGROUND AND RATIONALE

There are over 1 million people living with spinal cord injury (SCI) with devastating functional impairments including paralysis and bowel/bladder dysfunction.¹ Nearly every person with SCI develops neurogenic bladder.² The gold-standard treatment of neurogenic bladder involves the use of anticholinergic bladder medications, which suffers from non-compliance and adverse medication effects.³ Improving bowel and bladder function is the number one priority that people living with SCI wish to achieve.⁴ Treatments such as bladder neuromodulation with tibial nerve stimulation (TNS), have been shown to improve bladder function in SCI without adverse effects.^{5,6} Percutaneous TNS (PTNS) is performed using a needle inserted into the skin to direct the electric current, provided by trained healthcare workers in the clinic setting under physician supervision. This requires frequent visits in a population with known accessibility challenges. Transcutaneous TNS (TTNS) accomplishes the same goal, but uses non-invasive surface electrodes. However, this modality has only been performed in the clinic setting. There is currently a gap in our knowledge about the safety and feasibility of TTNS at home for bladder neuromodulation in SCI. The proposed research is innovative, in our opinion, because it represents a substantive departure from the status quo by using TTNS at home to replace anticholinergic medications and provide a dignified treatment that can improve quality of life.

Electric stimulation is routinely being used in neurorehabilitation. The PI has published reviews on the current state of rehabilitation in SCI, describing the use of FES and NMES in SCI for motor/sensory recovery, decreasing spasticity, and improving neuropathic pain.^{9, 10} Patients are routinely prescribed electric stimulation units for home use to help with motor recovery and strengthening. We propose the development of a protocol that uses the same equipment in a novel way to effect bladder function.

We are currently using the proposed TTNS protocol for research purposes (HSC-MS-15-0806) at TIRR for acute SCI during their inpatient rehabilitation admission (Table 1). Based on the preliminary safety data, we believe we can develop this protocol for home use (Table 2).

Table 1. Preliminary data demographics of subjects inpatient TTNS protocol

There have been 12 subjects recruited to the inpatient TTNS protocol with a variety of cervical and thoracic injuries, with subsequent complete and incomplete paraplegia and tetraplegia. Consecutive inpatients were screened and approached for the study. To date (7/12/2017), 11/12 patients that consented to the study completed the TTNS protocol and 1 (subject 12) has ongoing stimulation. There were no reported complaints about the TTNS. There were no adverse events directly related to the TTNS protocol, including worsening pain (numeric pain scale (NPS)), skin irritation, and bladder complaints (urinary tract infections, leaking, incontinence, etc).

Please note, the above subjects have all been acutely injured and are at higher risk for morbidity compared to chronic SCI subjects. Half of the UTIs occurred before subject recruitment, and half of the UTIs occurred about 1 week after completion of the stimulation protocol. None occurred during the TTNS protocol. Based on our inpatient experience with this TTNS protocol, the high compliance, lack of adverse events, and feasibility, we believe this protocol can be translated to the outpatient setting and performed by the subjects themselves and/or their caregivers.

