2.2. Primary Objectives

Primary Objective 1: Safety, feasibility, and compliance of TTNS at home.

Primary Objective 2: Overall satisfaction with TTNS based on survey.

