4. TRIAL SCHEDULE

Table 2. Timeline of protocol per subject

Weeks in Study Protocol

| Activities | 0 | W1 | W2 | W3 | W4 |
|--|---|---------|----|----|----|
| Clinic Enrolment: | | | | | |
| Eligibility screen | X | | | | |
| Informed Consent | X | | | | |
| Incontinence Questionnaire (I-QOL) | X | | | | |
| Side effect questionnaire | X | | | | |
| TTNS demonstration | X | | | | |
| Home | | | | | |
| Bladder diary | | □-----□ | | | |
| I-QOL | | | X | | X |
| TTNS | | □-----□ | | | |
| Discontinue bladder medication | | | X | | |
| Side effect questionnaire/ TTNS survey | | | | | X |

5. STUDY DESIGN (Table 2)

Anticipated number of patients to screen: 40

- Anticipated number of patient to enrol: 20
- Anticipated drop out or loss to follow-up: 4

Approximate time to complete study recruitment: 1 year

Expected duration of subject participation: 4 weeks

TTNS protocol: (please refer to protocol HSC-MS-15-0806) electrodes 2 inch by 2 inch will be placed according to anatomic landmarks, with the negative electrode behind the internal malleolus and the positive electrode 10cm superior to the negative electrode, verified with rhythmic flexion of the toes secondary to stimulation of the flexor digitorum and hallicus brevis. The intensity level will be set to the amperage immediately under the threshold for motor contraction. If there is not contraction seen, maximal tolerable intensity will be used. In addition, if the patient perceives pain, the intensity will be lowered until comfortable. Stimulation frequency of 10 Hz and pulse width of 200ms in continuous mode will be used.^{13, 14}

- Information gathered:
 - o Clinical demographics, morbidity, and Neurologic Exam findings from interview with subjects, exam, and EMR review.

- Bladder diary will include:
 - use of TTNS with amperage and presence of toe flexion, and pain score 0-10
 - log of catheterization, volumes
 - log of incontinence episodes
 - Description of other observed changes, including but not limited to: fatigue, vision changes, mental status, bowel program changes, and sexual function changes.
- Information will be tabulated on an Excel spreadsheet on my personal work desktop, password protected. Any paper data (bladder diary) will be de-identified and retained in a locked drawer in the locked office of the PI.

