6.4. Study Visits and Procedures

- *Screening Visits and Procedures*

Screening will be performed in the SCI clinic by the PI and co-I SCI attendings.

Those that meet the I/E criteria will be approached for the study by the PI and co-I attendings. They have until the study period is complete to decide whether they want to participate. However, they will have to return to clinic to have the TTNS trial performed and the directions for home use.

- *Study Visits and Procedures*

Subjects will have their first study visit after their normal clinic visit. Once consented, we will trial TTNS for a response of toe flexion. If they have a response, they will be included in the study. If no response or not tolerating electric stimulation, they will not be included in the study.

Participants will have direction in clinic on the use of the Stambil+, including written, oral, and smartphone images/video if they have access.

The electric stimulation protocol will use stimulation frequency of 10 Hz and pulse width of 200ms in continuous mode for 30 minutes daily, beginning as soon as possible. For sexually active women of child-bearing age, the home use will begin after the results of a pregnancy test are provided. The goal is daily use of TTNS for 4 weeks.

Subjects will be called weekly to capture the information from the bladder diary log and to monitor progress of protocol. They will also be reminded to change electrodes weekly.

- *Final Study Visit:*

Upon completion of the 4-week protocol, subjects will return with the stimulator and the bladder diary.

- *Post Study Follow up and Procedures*

The data will be statistically analysed in the post-study follow up. Subject participation is not required.

- *Discontinuation Visit and Procedures*

If withdrawal occurs, no evaluation will be required for the final study visit, regardless of the withdrawal reason. There are no safety risks in withdrawing from this study at any point.

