11.2. Statistical and Analytical Plans

This pilot study will serve as an earlier-phase developmental function that will enhance the probability of success in a larger subsequent randomization intervention trial.

In Aim 1, for safety, we hypothesize that there will be no unusual adverse events. However, because UTI is directly related to the bladder, we will focus on the occurrence of UTI. Based on literature, the overall rate of UTI in SCI is about 2.5 episodes per patient per year.¹⁸ As a result, we expect to see .2 episodes per patient during the 4-week study period. Based on that, we construct the stopping rules to stop at 20% UTI rate using lower 90% exact Blyth-Still-Casella confidence bounds. If the number of patients with UTI exceed 3 in the first 5 patients, 4 in the first 10 patients, or 5 in the 14 patients, then patient accrual will be paused pending a review by a medical advisory board comprised of SCI experts.

For feasibility and compliance, we will calculate descriptive statistics to determine the dropout rate and percent of adherence to the prescribed regimen as well as program satisfaction. If the dropout rate is less than 25%, and if subjects complete greater than 70% of daily TTNS use in the 4-week period, we will consider the study has high feasibility/adherence. If more than 80% of subjects report that they were satisfied with the program, then we will consider the study has high satisfaction.

In Aim 2, descriptive statistics will be provided for incontinence episodes, catheterization frequency, volumes voided, and anticholinergic-related side effects after the TTNS. The results along the time will be compared to baseline by paired t test, signed t test, or repeated measure methods when appropriate. Since this is an exploratory study and the efficacy of TTNS in this study will be further studied in future larger studies, Bonferroni correction will not be necessary. TTNS satisfaction will be based on the scores of a TTNS survey and descriptive analysis will be provided as well. We will also check the association between these changes from baseline, as well as bladder medication associations.

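### Scheduled UTI ascertainment stops with the 4 weeks of stimulation, so the study cannot show whether UTIs increase just afterwards, which is when the pilot reports its only post-recruitment UTIs

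*Combined protocol and SAP*

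**What the plan says.** Section 2.2 lists safety first: "Primary Objective 1: Safety, feasibility, and compliance of TTNS at home". Section 11.2 narrows it: "because UTI is directly related to the bladder, we will focus on the occurrence of UTI". Sections 2.4, 9.3 and 11.2 take a literature rate of 2.5 episodes per patient per year, convert it to 0.2 per patient over the 4-week study period, and build a rule on it that pauses accrual. UTI is the only safety outcome with such a rule.

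Observation is tied to stimulation. Stimulation is daily for 4 weeks (section 6.4), Table 2 ends at week 4, and section 5 gives "Expected duration of subject participation: 4 weeks". Subjects then hand back the stimulator and diary. On what follows, section 6.4 says: "The data will be statistically analysed in the post-study follow up. Subject participation is not required". It also requires no evaluation of subjects who withdraw.

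The pilot text in section 1 dates one half of its UTIs to the time before recruitment and says of the rest that "half of the UTIs occurred about 1 week after completion of the stimulation protocol". It adds: "None occurred during the TTNS protocol". It also cautions that "the above subjects have all been acutely injured and are at higher risk for morbidity compared to chronic SCI subjects".

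**The concern.** All the pilot UTIs reported after recruitment fell about a week after stimulation ended. The home study's schedule stops just short of the matching period, and the protocol gives no reason for stopping there. If UTI risk did rise once stimulation finished, neither the reported UTI rate nor the pause rule would reflect it. The safety result of a study meant to inform a larger trial would then describe the stimulation weeks only. Skin reactions and pain from stimulation are not affected, because they arise while the device is in use.

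**Working it through.** **Inputs.** UTI rate 2.5 per patient-year (sections 2.4, 9.3, 11.2). Enrolment 20, with 14 considered sufficient (section 11.1). Anticipated dropout 4 (section 5). Pause if patients with UTI exceed 3 of the first 5, 4 of the first 10, or 5 of 14 (section 9.3). Poisson counts at a constant rate are my assumption.

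**1. The plan's own figure.** 2.5 × 4/52 = 0.192 per patient, which rounds to the stated 0.2. The monitoring is therefore calibrated to the stimulation period alone.

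**2. What the 4-week window sees.** 20 × 0.192 = 3.8 expected background episodes (14 × 0.192 = 2.7). P(no UTI at all) = exp(−3.85) = 2% in 20 patients and exp(−2.69) = 7% in 14.

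**3. What it cannot see.** The background chance of at least one UTI in 4 weeks is 1 − exp(−0.192) = about 17.4%. An exact binomial recursion over the looks at 5, 10 and 14, reading exceed literally, gives a pause probability of 3.2%. Now assume a risk r in the week after stimulation. The true 5-week risk is 1 − (1 − 0.174)(1 − r).

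| Assumed risk r in week 5 | Risk over 5 weeks | Pause probability, 4-week count | Pause probability if week 5 were counted |
|---|---|---|---|
| 20% | 34% | 3.2% | 36% |
| 30% | 42% | 3.2% | 61% |
| 40% | 50% | 3.2% | 81% |

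The values of r are illustrative and are not estimates from the pilot. The third column does not move because the rule contains no information on week 5.

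**4. What two further weeks would add.** 2.5 × 2/52 = 0.096 per patient, or 1.9 in 20. Through week 6: 2.5 × 6/52 = 0.288 per patient, or 5.8 in 20.

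**5. How much weeks 5-6 could show on their own.** With mean 1.92, P(4 or more) = 12.9% and P(5 or more) = 4.6%, so 5 events is the smallest count that is unusual at the one-sided 5% level. If the true rate in those weeks were doubled (mean 3.85), P(5 or more) = 34%. If tripled (mean 5.77), it is 68%. If only 20 − 4 = 16 subjects were followed, background is 1.5, and a doubling gives 5 or more with probability 20%.

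**6. Why weeks 5-6 should be reported separately.** Against the pooled 6-week mean of 5.77, the smallest unusual count is 11 (P = 3.4%). A doubling confined to weeks 5-6 raises the pooled mean to 5.77 + 1.92 = 7.69, and P(11 or more) is then 15%, against 34% when those weeks are examined alone.

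**7. Why the pause boundaries should stay on 4 weeks.** At the background rate, the unchanged boundaries applied to a 6-week count (risk 25.0%) would pause with probability 13.2% instead of 3.2%.

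**The case against.** The strongest objection is that the pilot pattern carries little evidence. Half of its UTIs came before recruitment, which fits ordinary background occurrence. The number of events is not in the text available, so half could be a single event. The 12 patients were acute inpatients, whereas this trial requires at least 6 months of neurological stability (section 3.3). The pilot text also reports no adverse events directly related to TTNS, naming urinary tract infections among them. All of this stands.

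A reader might infer that the study would record no UTIs, that the pause rule could never trigger, or that the design lets TTNS be declared safe because nobody is looking. The documents do not support these readings. The first two need the pilot pattern to recur exactly, while the protocol's own rate makes zero UTIs in 20 patients about a 2% event. As to the third, section 11.2 sets thresholds for feasibility, adherence and satisfaction, but no rule that declares safety.

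Later UTIs might also surface through the medical-record review in section 5 or the quarterly morbidity review in section 9.3. Neither has a stated post-treatment window, so capture is possible but not planned. The study schedule and case report form are listed as attachments but are not available here, and could say more.

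Finally, extra follow-up in 20 uncontrolled patients will not settle whether an excess exists. That is correct, and it limits what may be claimed from the added data.

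**Conclusion.** The point holds in a limited form. Planned UTI ascertainment covers the stimulation weeks and nothing after them, and nothing in the available text supplies a later window. The design can therefore neither show nor give any reassurance about an excess after stimulation, even though the investigators' own pilot gives a modest reason to look there. It should not be read as evidence that stimulation delays UTIs.

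The omitted two weeks hold about 1.9 expected background episodes in 20 patients, half as many again as the 3.8 expected during stimulation. Following them would make a large excess visible but would usually miss a doubling. These figures rest on the protocol's 2.5 per patient-year, a constant rate, Poisson counts and all 20 subjects being reached. I rate this a cheap improvement, with moderate confidence.

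**What to change.** - **Schedule.** In Table 2 and section 6.4, add research-assistant phone calls at weeks 5 and 6 asking about UTI. Include subjects who withdrew, and record the date of the last stimulation session. Change participation in section 5 from 4 to 6 weeks.
- **Ascertainment.** Ask about UTI in the same way as during treatment. The available text gives no UTI definition, so one should be written and used throughout.
- **Pause rule.** Leave the boundaries on the 4-week count, to which the 0.2 reference applies. Supply the week 5-6 counts to the quarterly morbidity review, so that they are seen while the study runs. The pause rule itself will still not respond to events after week 4.
- **Reporting.** In section 11.2, report UTIs in weeks 5-6 separately against 0.096 per patient (about 1.9 in 20), and also the 6-week total against 0.29 per patient. State that both comparisons are descriptive.

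**Cost.** About 40 calls (2 × 20) by staff who already call weekly, two more weeks of participation without visits, changes to consent and schedule wording, and possibly a less favourable UTI count.

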1.1. General Introduction

The Stambil + is an electric stimulation unit used for the rehabilitation of those with paralysis. It is currently used at TIRR Memorial Hermann on nearly every patient with paralysis for the purposes of motor and sensory recovery. We are currently using the proposed TTNS protocol for research purposes (HSC-MS-15-0806) at TIRR for acute SCI during their inpatient rehabilitation admission. Based on the preliminary safety data, we believe we can develop this protocol for home use. The proposed protocol is using the device in a new way, to stimulate the nerves of the legs which is known to effect the bladder in a process described as “neuromodulation.”

The status quo as it pertains to the management of neurogenic bladder in SCI is anticholinergic medications to inhibit bladder activity, increase bladder capacity, and decrease detrusor pressures.⁴ However, management of neurogenic bladder requires further improvement, with an estimated 50% developing serious urologic complications.² Ongoing research regarding the neuromodulation of chronic neurogenic bladder is promising, demonstrating equal efficacy to current management without non-compliance and adverse medication side effects, with improved quality of life.⁵⁻⁸ Although neuro-modulation techniques are currently used for chronic neurogenic bladder, its use is limited to frequent clinic visits, imposing a barrier to a population known to have challenges accessing medical care. The proposed research is innovative, in our opinion, because it represents a substantive departure from the status quo by using transcutaneous tibial nerve stimulation in the home setting to improve bladder function. Rehabilitation horizons for neurogenic bladder management which have previously been unattainable through current efforts including the prevention of detrusor sphincter dyssynergia and related autonomic dysreflexia, maintenance of bladder capacity and compliance, and reduction in oral medication use with improved quality of life are also likely to become attainable.

Electric stimulation is currently being used in neurorehabilitation. The candidate has published reviews on the current state of rehabilitation in SCI, describing the use of FES and NMES in acute SCI for motor/sensory recovery, decreasing spasticity, and improving neuropathic pain.^{9, 10} Patients are routinely prescribed electric stimulation units for home use to help with motor recovery and strengthening. We propose the development of a protocol that uses the same equipment in a novel way to effect bladder function.

1.2. Rationale and justification for the Study

We have selected a neuromodulation technique, TTNS, that has been used safely in chronic SCI with good results for improving quality of life and bladder parameters and have developed a protocol for home use.

Specific Aim 1: **Determine the safety, feasibility, and compliance of a daily home TTNS protocol in chronic SCI provided by self or caregiver for 4 weeks.**

Hypothesis 1.1: TTNS at home is safe and feasible with high compliance.

Hypothesis 1.2: TTNS protocol will demonstrate overall satisfaction as a neurogenic bladder treatment option based on survey questionnaire.

Specific Aim 2. **Determine the efficacy of a 4 week TTNS protocol.**

Hypothesis 2.1: Incontinence quality of life scores and frequency of incontinence will improve with TTNS compared to their baseline.

Hypothesis 2.2: Frequency of catheterization and volumes voided will improve with TTNS compared to baseline measurements.

Hypothesis 2.3: Anticholinergic-related side effects will improve with TTNS after discontinuation of bladder medications

a. Rationale for the Study Purpose

Neuromodulation techniques have been safely used for improving neurogenic bladder in chronic SCI for many years. However, bladder neuromodulation is only being performed in the clinic setting requiring frequent visits, limiting its use in a population known to have high healthcare costs and barriers to accessing medical care. Based on our experience, we believe we can develop a home-based protocol.

Gaps in the knowledge which we intend to fill are:

- 1) Safety, feasibility, and compliance of a home TTNS protocol in chronic SCI.
- 2) Efficacy of a 4-week TTNS protocol in SCI based on the Incontinence Quality of Life (I-QOL), which will provide effect size to power future studies.

b. Rationale for Doses Selected

Based upon an extensive review of the literature on neuromodulation of neurogenic bladder and the clinical experience of the mentorship team, we believe a TTNS protocol over a 4 week period will improve continence. Tibial nerve stimulation protocols use submotor current intensity with a duration of 200 μ s and frequency of 10Hz.^{13,14} Increasing the treatment frequency dramatically shortens the time required for response while maintaining efficacy, varying from 6-12 sessions.¹⁴

c. Rationale for Study Population

Participants will include consecutive SCI subjects at the SCI clinic who meet the I/E criteria (Table 1) and consent to the protocol.

d. Rationale for Study Design

Based on our current inpatient experience, we believe this protocol can be performed safely at home by subjects and/or their caregivers if given detailed instructions. Subjects who perform intermittent catheterization are being selected because they more likely to have incontinence

than those with an indwelling catheter. If patients are interested, we will trial stimulation in clinic. We will exclude those who we cannot produce toe flexion with posterior tibial nerve stimulation. After 1 week of home stimulation, those that are on bladder medicine will discontinue the medication. There is no other harm from rapid discontinuation of bladder medication, except for incontinence. We expect that incontinence will be reduced from this first week of TTNS. The I-QOL questionnaire is administered at baseline, and at the end of 2 and 4 weeks to determine when best effects of TTNS are achieved.

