2.3. Secondary Objectives

Secondary Objective 1: I-QOL scores will improve and incontinence episodes will reduce after TTNS compared to baseline.

Secondary Objective 2: The frequency of catheterization and the volumes voided will improve with TTNS compared to baseline based on bladder diary.

Secondary Objective 3: Anticholinergic side effects will be reduced based on survey after TTNS protocol.

2.4. Potential Risks and Benefits:

a. End Points - Efficacy

Specific Aim 1: No efficacy requirement for the safety and feasibility studied in specific aim 1.

Specific Aim 2: We expect improved I-QOL scores compared to baseline. As a pilot trial, we have not powered the study for this measure. Results from this study will provide effect size to power a larger study.

b. End Points - Safety

Urinary Tract Infection (UTI) risk:

We expect the rates of morbidity to be the same between those who participate and those who do not. However, because UTI is directly related to the bladder, we will focus on the occurrence of UTI. Based on literature, the overall rate of UTI in SCI is about 2.5 episodes per patient per year. As a result, we expect to see 0.2 episodes per patient during the 4-week study period. Based on that, we construct the stopping rules to stop at 20% UTI rate using lower 90% exact Blyth-Still-Casella confidence bounds. If the number of patients with UTI exceed 3 in the first 5 patients, 4 in the first 10 patients, or 5 in the 14 patients, then patient accrual will be paused pending a review by a medical advisory board comprised of SCI experts.

Bladder medication discontinuation risk:

- Worsened incontinence

Electric Stimulation Risks:

Electric stimulation is commonly performed on the extremities of those with spinal cord injury at the study institution. There are few adverse reactions to electric stimulation. The common ones include:

- Pain with electric stimulation: in these cases, the intensity is reduced until it is comfortable.
- Skin irritation: it is common for redness to occur on the skin at the site of the surface electrode. This typically dissipates within an hour of removing the electrode. In some cases, the redness remains the next day. In these cases, they are likely sensitive to the adhesive used and a hypoallergenic skin electrode will be provided.

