3.5. Withdrawal Criteria

Possible reasons for discontinuation of study intervention:

- Intolerable incontinence after discontinuation of bladder medications
- Intolerant to electric stimulation
- Non-compliance

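### The protocol names incontinence as the only harm of the planned drug stop and asks for no check at withdrawal, though its own background says the drug also acts on bladder capacity and pressure

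*Combined protocol and SAP*

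**What the plan says.** The drug stop is part of the regimen. Section 1.2 d has subjects on a bladder drug discontinue it after one week of home stimulation, and Table 2 marks the stop under W2. On the risk of stopping, section 1.2 d says: "There is no other harm from rapid discontinuation of bladder medication, except for incontinence". Section 2.4 b has a single bullet under medication discontinuation: "Worsened incontinence".

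Section 1.1 describes standard management as "anticholinergic medications to inhibit bladder activity, increase bladder capacity, and decrease detrusor pressures". Hypothesis 2.3 ties the drugs being stopped to anticholinergic side effects.

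Section 3.5 gives as a possible reason for ending the intervention "Intolerable incontinence after discontinuation of bladder medications". For subjects who leave, section 6.4 says: "If withdrawal occurs, no evaluation will be required for the final study visit, regardless of the withdrawal reason". It adds: "There are no safety risks in withdrawing from this study at any point".

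**The concern.** The risk statement is categorical, and it is narrower than the protocol's own account of what the drug does. If a drug is given partly to raise capacity and lower pressure, stopping it may give up those effects. Neither appears as a risk, so investigators work from an incomplete statement, and so do subjects if the consent form repeats it.

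The withdrawal rule makes this matter for the data. Subjects who tolerate the drug stop worst are among the likeliest to leave, and for them the plan asks for no safety information at exit. Safety is in Primary Objective 1. A safety summary that is least complete for those who did worst off drug will tend to look better than it should.

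**Working it through.** The plan gives no figure for this risk, so the check is mainly a comparison of sections.

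1. **Drug effects against listed risks.** Section 1.1 names three effects: less bladder activity, more capacity, lower detrusor pressure. Sections 1.2 d and 2.4 b list one consequence of stopping: incontinence. Loss of capacity control and loss of pressure control are not listed as discontinuation risks in any section supplied.

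2. **Time off drug.** The protocol lasts 4 weeks. With a stop after week 1 (section 1.2 d), 4 − 1 = 3 weeks are off drug. If the W2 mark in Table 2 is read as the end of week 2, 4 − 2 = 2 weeks. Section 1.2 d favours the first reading. The plan does not ask for each subject's actual stop date.

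3. **Stimulation before the stop.** With daily use, 7 × 1 = 7 sessions come before a stop after week 1, and 7 × 2 = 14 before a stop at the end of week 2. The cited sessions to response are 6–12 (section 1.2 b) and 6–8 (section 8.1). Seven lies inside both ranges, near the low end of the first. The protocol does not say that response there means restored capacity or pressure, and section 1.2 d expects only incontinence to fall in the first week.

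4. **Safety information during participation.** General capture exists:
   - adverse events are broadly defined and collected by the research assistant and the investigator (sections 9.1 and 9.2);
   - the diary has an open field for other changes and logs catheterization volumes (section 5);
   - a weekly call collects the diary data (section 6.4);
   - section 5 also gathers "Clinical demographics, morbidity, and Neurologic Exam findings from interview with subjects, exam, and EMR review";
   - bladder medications are recorded (section 8.6), without a stated stop or restart date.

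5. **Safety information at withdrawal.** Section 6.4 waives evaluation for every withdrawal reason. None of the sources in step 4 is stated to extend to the point of withdrawal or beyond. Nothing bars restarting the drug, but no contact at exit is planned to ask about it.

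6. **How many subjects.** Section 5 anticipates 20 enrolled and 4 lost, which is 4/20 = 20%. The documents do not say how many losses would follow the drug stop. Within that planning figure the number runs from 0 to 4. This is a range of possible missing outcomes, not an estimate of harm.

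**The case against.** The strongest reply is that the protocol says what the drug does, not that losing the effect for 2 to 3 weeks is harmful. That is correct: harm is an inference, and the risk wording should say *may*.

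The second reply is that the drug is being replaced, not simply removed. The background (section 1) presents home TTNS as a substitute for anticholinergics. Section 1.1 reports neuromodulation to be as effective as current management and expects capacity and compliance to be kept up. The stop also comes after a number of sessions inside both cited response ranges. This is a fair reason for the design, but not for denying any other risk: the efficacy of this home regimen is what Aim 2 examines, and section 2.4 a says the study is not powered for I-QOL, the Aim 2 measure discussed there.

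Third, much is already recorded, including catheterization volumes (which bear on capacity) and bladder medications. This stands for subjects still taking part. A reader might infer that the drug stop goes unmonitored, and the documents do not support that. The gap is at withdrawal.

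Fourth, the sentence in section 6.4 is about leaving the study, and the visit it waives is described only as returning the stimulator and diary. That also stands. Yet some who leave will already have stopped their drug on the protocol's instruction, so the blanket statement does not fit them.

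Finally, section 3.4 excludes patients on several bladder drugs, which narrows the group at risk but leaves those on one.

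**Conclusion.** The point holds as a should-fix item. The harm of the drug stop is stated too absolutely, and section 6.4 allows the safety outcome and restart status of subjects who leave after the stop to go unrecorded. No sample size, stopping rule or planned comparison is shown to be wrong.

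The size is qualitative. The documents give no event rate and no share of subjects on a drug. The conclusion assumes that the drug stopped is an anticholinergic, as Hypothesis 2.3 suggests, and that the case report form, diary and consent form (not supplied) do not already close the gap. If they do, the wording in sections 1.2 d, 2.4 b and 6.4 still needs correcting.

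A reader might go further and infer that stopping the drug exposes subjects to autonomic dysreflexia. Section 1.1 does speak of "prevention of detrusor sphincter dyssynergia and related autonomic dysreflexia", but as a hoped-for gain from better management. It links dysreflexia to dyssynergia, not to drug withdrawal. The documents do not support that stronger claim, nor a claim that subjects will be harmed.

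**What to change.** 1. In sections 1.2 d and 2.4 b, say that stopping the drug may worsen incontinence and may reduce control of bladder pressure and capacity. Align the consent form if it repeats the narrower risk.
2. In section 6.4, qualify the no-risk statement for subjects who have stopped their drug. Make one phone contact when such a subject withdraws, recording adverse symptoms and whether the drug was restarted. Count these subjects in the Aim 1 safety summary in section 11.2, including those replaced under section 3.6.
3. Record each subject's actual drug stop date.

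The cost is a wording amendment, one date field and one extra call per such withdrawal. No new procedure or visit is needed. I do not propose a pressure measurement, a dysreflexia item or a week-by-week symptom analysis, because the documents do not establish the link these would need. Any clinical rule on restarting the drug is for the investigators.
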